10.7.3 Unsolicited Adverse Events and Serious Adverse Events

Diaries will also be used for collection of unsolicited AEs in the week before the first vaccination as well as on each vaccination day and the following 28 days. In addition, subjects will be contacted by phone to verify whether they had any health concerns since the last visit.

The occurrence of AEs (serious and non-serious) will be assessed by non-directive questioning of the subject at each visit. AEs volunteered by the subject during or between visits in the diary or detected through observation, physical examination, laboratory tests, or other assessments during the entire trial, will be recorded in the eCRF, if they fall within the reporting period. Subjects should be instructed to report immediately any AEs with serious symptoms, subjective complaints or objective changes in their well-being to the Investigator or the site personnel, regardless of the perceived relationship between the event and the trial vaccine.

The Investigator will assess the relationship between trial vaccine and each occurrence of AE/SAE.

SAEs and AEs leading to vaccine withdrawal or trial discontinuation will be collected throughout the trial.

10.7.4 Adverse Events of Special Interest (AESI)

The following events will be considered as AESIs during this trial:

- AEs with a suspected immune-mediated etiology (see Appendix 1 Potential Immune-Mediated Diseases).
- Other AEs relevant to SARS-CoV-2 vaccine development or the target disease (see Appendix 2 for the current list of AESIs and see the protocol for details on laboratory testing for COVID-19).
- Non-serious intercurrent medical conditions that may affect the immune response to vaccination will also be collected throughout the trial.

AESIs will be collected throughout the trial.

10.7.5 Medically-Attended Adverse Events

Medically-attended AEs will be collected on the eCRF throughout the trial.

10.7.6 Grade 3 Adverse Reactions

Adverse reactions are defined as solicited local Grade 3 AEs, and solicited systemic or unsolicited Grade 3 AEs considered as related to the trial vaccine.

10.7.7 Adverse Events Related to Standardised MedDRA Queries

Subjects' AEs are filtered with Standard MedDRA Query (SMQ) for the following SMQs:

- Anaphylactic reaction (SMQ)
- Convulsions (SMQ)
- Embolic and thrombotic events (SMQ)
- Hypersensitivity (SMQ)
- Immune-mediated/autoimmune disorders (SMQ)
- Liver related investigations, signs and symptoms (Sub-SMQ)

In addition, two customized MedDRA queries are defined for taste and smelling disorder and events related to paraesthesia, hypoesthesia, and hyperesthesia. The related terms are listed in the Appendix 3 MedDRA Terms for CMQs. The MedDRA SMQs for the specific terms are not included in the appendix. See official MedDRA documentation.

10.7.8 Definition of Subjects with asymptomatic SARS-CoV-2 infection

Subjects without a AESI indicating COVID-19 infection and a positive SARS-CoV-2 N protein result and/or a positive PCR result.

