## 6.2 Exclusion Criteria

Subjects will not be enrolled in this trial if they meet **any** of the exclusion criteria.

1. A previous clinical and laboratory-confirmed diagnosis of COVID-19 within the last six months prior to screening.
2. Use of any investigational or non-registered product (vaccine or drug) other than the trial vaccine within 28 days preceding the administration of the trial vaccine, or planned use during the trial period.
3. Receipt of any other vaccines within 28 days prior to enrollment in this trial or planned receipt of any vaccine within 28 days of trial vaccine administration. Planned vaccination with an inactivated influenza vaccine is permitted.
4. Receipt of any investigational, authorized or licensed SARS-CoV-2, other coronavirus vaccine or any other LNP-containing mRNA vaccine prior to the administration of the trial vaccine. For authorized or licensed SARS-CoV-2: planned administration during the trial up to 6 weeks after the foreseen date of second dose administration of CVnCoV.
5. Any treatment with immunosuppressants or other immune-modifying drugs (including, but not limited to, corticosteroids, biologicals, and methotrexate) for >14 days in total within 6 months prior to the administration of the trial vaccine or planned use during the trial. For corticosteroid use, this means prednisone or equivalent, 0.5 mg/kg/day for 14 days or more. The use of inhaled, topical, or localized injections of corticosteroids (e.g., for joint pain/inflammation) is permitted.

Note: This exclusion does not apply to the renal transplant cases and is at the Investigator's discretion for subjects with other co-morbidities (e.g., COPD).

6. Any medically diagnosed or suspected immunosuppressive or immunodeficient condition based on medical history and physical examination, excluding the co-morbidities specified in Section 6.3.

(Subjects with chronic HIV infection with controlled Hep B infection with therapy or aviremic Hep C may be eligible for the trial, based on the Investigator's judgment).

7. History of immune-mediated or autoimmune disease.
8. History of anaphylaxis or allergy to any component of CVnCoV or aminoglycoside antibiotics.

9. History of or current alcohol and/or drug abuse.
10. History of confirmed SARS or MERS disease
11. Administration of immunoglobulins and/or any blood products within the 3 months preceding the administration of any dose of the trial vaccine.

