### **9.2.2 Antibody Responses to SARS-CoV-2 (N Protein)**

Antibody responses to SARS-CoV-2 will be evaluated for all subjects by measuring the binding antibodies to the SARS-CoV-2 N protein (virus antigen not contained in the vaccine construct) at the time points specified in Table 1, and will be performed by an immunoassay.

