7.3 Exploratory Objectives

- To evaluate the occurrence of laboratory-confirmed cases of COVID-19 after 1 and 2 doses of CVnCoV.

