
Occurrence of confirmed COVID-19 cases
 
Number of subjects with reverse transcription polymerase chain reaction (RT-PCR)-confirmed SARS-CoV-2 infection as measured by RT-PCR at clinically determined time points throughout the trial.
 
Number of subjects with asymptomatic SARS-CoV-2 infection as measured by serological titers of nucleocapsid antibodies on Day 1, Day 43, Day 120 and Day 393.
	
In subjects who received at least one dose of CVnCoV vaccine and a post baseline vaccine safety assessment is available. Subjects receiving an authorized/licensed COVID-19 vaccine during the course of the trial will be censored at the day after intake.
 
Number and percentage of subjects by co-morbidity at baseline and post-baseline time points with a positive RT-PCR result. This exploratory endpoint will be analyzed with the safety analysis set.
 
Number and percentage of subjects by co-morbidity at baseline and post-baseline with a positive RT-PCR result and/or infection defined by SARS-CoV-2 N-antigen and no COVID-19 symptoms. This exploratory endpoint will be analyzed with the immunogenicity set. Day 211 and Day 393 will not be measured.

	
CMI responses will not be analysed.

ENDPOINTS (subject level)	ESTIMANDS (population level)

CMI response
 
On Day 1, Day 29, Day 43 and Day 120 in peripheral blood stimulated with antigen in a subset of subjects*:
 
The SARS-CoV-2 S-specific T cell response, as measured by cytokine and chemokine expression after antigen stimulation using a standardized whole blood collection and culture system.
	

* The subset of subjects to participate in neutralizing activity and CMI response testing shall consist of approximately 25 subjects for each co-morbidity (up to a maximum of 175 subjects).

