10.8 Immunogenicity Assessments

10.8.1 Seroconversion

Seroconversion is defined by a relevant increase in antibody titer compared to baseline. The titer is the highest dilution factor that still yields a positive reading for the antibodies. I.e. larger titers correspond to larger concentration of antibodies. Depending on the type of antibodies and previous exposure of a subject to SARS-CoV-2 (as measured by antibodies to the SARS-CoV-2 N protein), different definitions of seroconversion will apply.

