12.7.3 Exploratory Endpoints

The below mentioned exploratory endpoints will be included in the abbreviated scope. Cell-mediated immune response and cytokine concentrations will not be included.

- Number of subjects and percentages with RT-PCR-confirmed SARS-CoV-2 infection at clinically determined time points throughout the trial will be tabulated by time point. This table and listing will be presented for the safety set.
- Number of subjects and percentages with asymptomatic SARS-CoV-2 infection as measured by serological titers of nucleocapsid antibodies on day 1, day 43 and day 120 will be tabulated by time point. Subjects with COVID-19 symptoms are excluded.

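### The asymptomatic-infection table does not require a negative N-antibody result on Day 1, so its Day 43 and Day 120 counts cannot separate new infections from those that predate the trial

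*SAP*

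**What the plan says.** The working definition is in SAP 10.7.8: "Subjects without a AESI indicating COVID-19 infection and a positive SARS-CoV-2 N protein result and/or a positive PCR result". SAP 12.7.3 says that "asymptomatic SARS-CoV-2 infection as measured by serological titers of nucleocapsid antibodies on day 1, day 43 and day 120 will be tabulated by time point", and removes only subjects with COVID-19 symptoms. The estimand in SAP 9.4 counts subjects "at baseline and post-baseline with a positive RT-PCR result and/or infection defined by SARS-CoV-2 N-antigen and no COVID-19 symptoms". Table 14.2.6.1 in SAP Appendix 4 names the same three days and uses the per protocol immunogenicity set (PPI).

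On entry, Protocol 6.2 excludes "A previous clinical and laboratory-confirmed diagnosis of COVID-19 within the last six months prior to screening". The eligibility criteria contain no N-antibody screen. Protocol 9.2.2 describes N as a "virus antigen not contained in the vaccine construct", so a positive result marks infection, not vaccination. SAP 10.8.1 itself treats N antibody as the measure of earlier exposure.

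The related objective in SAP 7.3 is "To evaluate the occurrence of laboratory-confirmed cases of COVID-19 after 1 and 2 doses of CVnCoV".

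**The concern.** Subjects with an older or undiagnosed infection may enrol, and some will be N-positive on Day 1. Nothing in the definition asks whether positivity is new. A subject who stays positive meets it on Day 1, Day 43 and Day 120.

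The objective concerns what happens after one and two doses. The trial has a single arm, so no control group shares the baseline prevalence and lets a reader allow for it. A Day 43 or Day 120 percentage made up largely of old infections could be read as infection despite vaccination.

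The word asymptomatic is also insecure. The Schedule of Activities in Protocol Section 2 marks AESI collection from Day 1, so the AESI condition cannot detect a symptomatic illness before the trial. SAP 12.7.3 does not say whether its symptom exclusion reaches back before Day 1. If it does not, a subject who was ill with COVID-19 more than six months before screening and is still N-positive would be labelled asymptomatic.

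**Working it through.** **Text check.** Three conditions could separate new from old infection: a negative N result on Day 1, a negative-to-positive change, or onset after dose 1. None appears in SAP 10.7.8, 9.4 or 12.7.3, in the title of Table 14.2.6.1, or in Protocol 4.2.3, where the endpoint is defined.

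**Illustration.** The plan gives no figure for baseline N-positivity, persistence or new infection, so there is nothing to reproduce. The only documented input is N = 129 enrolled (SAP 6.3). The rest are assumptions:

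- p, N-positive on Day 1: 2% to 20%
- s, share of those still positive at the later visit: 70% to 100%
- r, new asymptomatic infection among Day 1 N-negatives: 1% to 3%

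Old positives counted = N × p × s. New infections = N × (1 − p) × r. Inflation = (old + new) / new = 1 + p × s / [(1 − p) × r].

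| p | s | r | Old | New | Counted | Share old | Inflation |
|---|---|---|---|---|---|---|---|
| 2% | 70% | 3% | 1.8 | 3.8 | 5.6 | 32% | 1.5 |
| 5% | 100% | 1% | 6.5 | 1.2 | 7.7 | 84% | 6.3 |
| 10% | 70% | 3% | 9.0 | 3.5 | 12.5 | 72% | 3.6 |
| 10% | 100% | 1% | 12.9 | 1.2 | 14.1 | 92% | 12.1 |
| 20% | 100% | 1% | 25.8 | 1.0 | 26.8 | 96% | 26.0 |

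The first and last rows are the extremes, because the share rises with p and s and falls with r. In the fourth row the table as planned would show 14.1/129 = 10.9%. Restricted to Day 1 negatives it would show 1.2/116.1 = 1.0%.

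**With no new infection at all** (r = 0), the post-baseline count would still be N × p × s: 1.8 to 2.6 subjects at p = 2%, 4.5 to 6.5 at 5%, 9.0 to 12.9 at 10%, and 18.1 to 25.8 at 20%.

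**Can the Day 1 row be subtracted?** In the third row Day 1 shows 129 × 0.10 = 12.9 and the later visit shows 12.5. The difference is −0.4, although 3.5 subjects were newly infected. Subtraction fails once some baseline positives revert.

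**Base.** Counts out of 129 are upper figures. Table 14.2.6.1 uses the PPI, which needs both doses in window and a sample from Day 43 onwards (SAP 9.5.2). Data are censored after an authorised vaccine (SAP 10.9), and immunogenicity draws stop then (SAP 6.2, Table 2, note j). The shares and inflation factors do not depend on N.

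**The case against.** A reader might infer that the SAP presents its Day 43 and Day 120 rows as infections after vaccination. It does not. The protocol endpoint includes Day 1, the estimand covers baseline and post-baseline, and the table is by time point. Read literally, it shows N-positivity among symptom-free subjects at each visit, and a persisting positive is then not an error. This stands. What remains is that such a table cannot speak to an objective framed as occurrence after dosing. Even that link is loose: the objective names laboratory-confirmed COVID-19, which Protocol Appendix 4 defines as RT-PCR-confirmed illness with symptoms.

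The information is also not lost. Appendix 4 of the SAP includes by-subject listings of N results (16.2.6.5) and of asymptomatic infection (16.2.6.8), and with at most 129 subjects a careful reader could trace Day 1 status. That shows that the repair is feasible, but it leaves the summary counts and denominators as they are.

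Finally, the table may never be produced. SAP 6.4 states that the analysis of confirmed COVID-19 occurrence is dropped, and Protocol 4.2.3 and SAP 9.4 list the asymptomatic endpoint under that heading. SAP 12.7.3 and Appendix 4 keep it. The documents do not settle this.

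**Conclusion.** The gap is real and follows from the text alone: the post-baseline counts overstate new infection whenever a baseline positive persists. On the assumed ranges, 32% to 96% of those counted after baseline would be pre-trial infections, an inflation of about 1.5 to 26 times. Those figures show only how sensitive the table is. The documents support no single multiple and no firm number of misattributed subjects.

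A reader might also conclude that past symptomatic illness will certainly be called asymptomatic. That is only possible, because the reach of the symptom exclusion in SAP 12.7.3 is not stated.

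The endpoint is exploratory and descriptive, with no test or sample size attached. The change is worth making, at modest priority.

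**What to change.** In SAP 10.7.8, 12.7.3 and Table 14.2.6.1:

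- Report N-positivity on Day 1 as baseline prevalence only.
- For Day 43 and Day 120, count subjects N-negative on Day 1 who are N-positive by that visit, or who have a first positive RT-PCR after dose 1, without COVID-19 symptoms. State that the count is cumulative, so that a subject appearing in both rows is understood as one infection.
- Use as denominator the Day 1 N-negative subjects with a result at that visit.
- Say whether the symptom exclusion covers illness before Day 1.

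Two inconsistencies need settling in the same edit. SAP 6.4 says that the analysis is not performed, while 12.7.3 and Appendix 4 keep it. SAP 9.4 assigns the immunogenicity set, while Table 14.2.6.1 uses the PPI.

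The cost is a few sentences in the SAP and one filter in the table program. N antibody is already measured on Day 1 under the Schedule of Activities in Protocol Section 2, so no new data are needed.

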10.7.9 Credibility Interval and related Estimate

The estimate, using Beta(α, β), is calculated as follows:

- $(\text{number of reactions} + \alpha) / (\text{total number of subjects} + \alpha + \beta)$.

The lower and upper intervals are calculated as follows for a given number of reactions:

- In the programming language SAS: betainv(0.025, number of reactions + α , total number of subjects – number of reactions + β) and betainv(0.975, number of reactions + α , total number of subjects – number of reactions + β).

The SAS programming language function betainv returns a quantile from the beta distribution.

10.8 Immunogenicity Assessments

10.8.1 Seroconversion

Seroconversion is defined by a relevant increase in antibody titer compared to baseline. The titer is the highest dilution factor that still yields a positive reading for the antibodies. I.e. larger titers correspond to larger concentration of antibodies. Depending on the type of antibodies and previous exposure of a subject to SARS-CoV-2 (as measured by antibodies to the SARS-CoV-2 N protein), different definitions of seroconversion will apply.

10.8.1.1 SARS-CoV-2 RBD of S Protein Antibodies

Seroconversion is defined as a fold increase above 1 in antibody titer against SARS-CoV-2 RBD of S protein regardless of the serostatus at baseline. In addition, 2-fold and 4-fold increases will be presented.

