	

• The number and percentage of subjects SARS CoV-2 seronegative at baseline for whom a seroconversion is observed will be summarized and presented at each blood sampling time point after baseline with exact 95% CI. Seroconversion is defined as detectable antibodies in the serum [<math>\geq</math> lower limit of quantification (LLOQ)].

 
Data will be presented after each vaccine dose.
 
Missing Data/Discontinuation
 
Concentration values of RBD and neutralizing antibodies marked as below the lower limit of quantification (LLOQ) will be set to 0.5*LLOQ. No imputation of missing values will be performed for any analysis (except the imputation for missing partial dates of AEs and concomitant medication).
 
Currently no replacement of discontinued or withdrawn subjects is foreseen. This plan may be affected if an important percentage of subjects opt to receive any of the authorized/licensed COVID-19 vaccines, in which case enrollment of additional subjects into this trial will be considered.

--	---

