## 10.3 Statistical Analyses

### 10.3.1 General Considerations

All data obtained in this trial and documented in the eCRF will be listed and summarized with sample statistics or frequency tables as appropriate. The safety and immunogenicity analyses will be done overall.

An SAP will be prepared and finalized at the latest prior to database lock. This document will provide further details regarding the definition of analysis variables and analysis methodology to address all trial objectives and the handling of missing data.

Subjects will be stratified post-hoc by pre-defined co-morbidities. Subjects with multiple co-morbidities will contribute to the different corresponding strata.

Data from this trial may be pooled with data from potential follow-up trials.

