#### 10.3.5.2 Primary Immunogenicity Analysis

No formal hypothesis on immunogenicity will be tested. Descriptive statistics for the immunogenicity endpoints will be provided.

The following analyses will be done for SARS-CoV-2 RBD of the S protein antibody concentrations and for neutralizing antibodies titers:

- Geometric mean concentrations (GMC) / GMT by group will be summarized with their 95% CI at each blood sampling time point for all evaluable subjects and then separately in subjects seronegative at baseline and in subjects seropositive at baseline.
- The fold change from baseline will be computed for seropositive subjects at baseline and geometric mean of the fold change (GMFC) by group will be displayed with their 95% CI at each blood sampling time point after baseline.
- The number and percentage of subjects SARS-CoV-2 seronegative at baseline for whom a seroconversion is observed will be summarized and presented at each blood sampling time point after baseline with exact 95% CI. Seroconversion is defined as detectable antibodies in the serum [ $\geq$  lower limit of quantification (LLOQ)].

Concentrations/titers marked as below the LLOQ will be arbitrary replaced by half of the LLOQ for GMC/GMT and GMFC computations purpose.

The analyses of CMI in terms of induction by the vaccine of SARS-CoV-2 S protein-specific T-cell responses will be detailed in the SAP.

Additional immunogenicity analyses including graphs will be described in the SAP as applicable.

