2.0 Change History

Version/Date	Change Log
1.0	Final version
2.0	
Implementing changes to schedule of visits based on Protocol Amendment #1 – Section 6.1 and 6.2
 
Description of the reduced scope – Section 6.1 and 6.2
 
Definition of seroconversion changed to an increase above 1 regardless of a subjects serostatus at baseline – Section 10.8.1
 
Removal of any interim analysis – Section 11.1
 
List of detailed scope of analyses related to abbreviated CSR – Appendix 4 List of Abbreviated Scope Based on SAP Version 2.0

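### The SAP's primary Day 43 seroconversion rate counts any titre rise in every subject, while the protocol's rate is restricted to baseline-seronegative subjects reaching the LLOQ, and the SAP plans no split by baseline serostatus

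*SAP*

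**What the plan says.** **Protocol.** The Synopsis reports the number and percentage of "subjects SARS CoV-2 seronegative at baseline for whom a seroconversion is observed", and section 10.3.5.2 repeats this. Both define seroconversion as detectable antibody, meaning a titre at or above the LLOQ. Section 10.3.5.2 also summarises GMC/GMT for all evaluable subjects and then "separately in subjects seronegative at baseline and in subjects seropositive at baseline". Baseline-seropositive subjects have their own summary: "The fold change from baseline will be computed for seropositive subjects at baseline", reported as GMFC.

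**SAP version 2.0.** Section 10.8.1.1 reads: "Seroconversion is defined as a fold increase above 1 in antibody titer against SARS-CoV-2 RBD of S protein regardless of the serostatus at baseline". Section 10.8.1.2 gives the same rule for neutralizing antibodies, and 12.7.2 makes it the primary Day 43 endpoint in the per protocol immunogenicity subset. Rates for 2-fold and 4-fold rises are added. The change history in section 2.0 records: "Definition of seroconversion changed to an increase above 1 regardless of a subjects serostatus at baseline". It gives no reason.

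**Within the SAP.** The lead-in in 10.8.1 asks for a relevant rise over baseline and says that definitions will differ by antibody type and by prior exposure as shown by N-protein antibody. The two subsections that follow give one rule for everyone. Sections 12.0 and 12.7.2 plan summaries by co-morbidity and overall and do not mention serostatus. No immunogenicity table title in Appendix 4 mentions it either.

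**The concern.** Becoming antibody-positive and rising above an existing titre are different events. The protocol keeps them apart; the SAP pools them under one name. Subjects with antibody on Day 1 can be in the trial, because the only infection-related bar on recent COVID-19 is "A previous clinical and laboratory-confirmed diagnosis of COVID-19 within the last six months prior to screening". Older or undiagnosed infection does not exclude. Under the SAP such a subject is a seroconverter if the Day 43 titre exceeds the Day 1 titre by any amount, so ordinary assay variation can decide the result. The 2-fold and 4-fold rates are pooled over serostatus as well and do not separate the groups.

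In a descriptive trial the reported rate is the result. A reader who takes the Day 43 figure for the protocol's rate may be misled in either direction.

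**Working it through.** **1. The plan's own figures.** Protocol Table 4 (SAP Table 3) uses a Beta(1.9, 0.1) prior. For 142 of 150 the estimate is (142 + 1.9)/(150 + 2) = 94.7%, with 95% interval 90.6 to 97.6, as printed. All ten entries reproduce. The arithmetic is sound; the question is what goes into the count.

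**2. Where the two rules differ.** SAP 10.5 sets values below the LLOQ to half the LLOQ. Suppose this applies to the final reported titre. A subject below the LLOQ on Day 1 then has a ratio of 0.5/0.5 = 1 if still below, and at least 1/0.5 = 2 if at or above. Both rules score that subject the same way, so the whole difference comes from subjects with a quantifiable Day 1 titre.

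The condition matters. SAP 10.8.2 forms titres as geometric means of duplicates, and 10.5 does not say at which level the substitution is made. At replicate level, one duplicate at the LLOQ and one below it give √(1 × 0.5) = 0.71 × LLOQ. The ratio is 0.71/0.5 = 1.41: a seroconverter under the SAP, but below the LLOQ under the protocol.

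**3. Size of the shift.** Let s be the seropositive share, p the conversion rate in seronegatives and q the share of seropositives with any rise. The pooled rate is (1 − s)p + sq, so

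pooled − protocol = s(q − p).

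The documents give none of s, p or q. For illustration, take all 129 enrolled subjects (SAP 6.3), although the per protocol subset will be smaller, and assume 26 seropositive (20%) and 103 seronegative.

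| Seronegatives converting | Seropositives rising | Pooled SAP rate | Shift (points) |
|---|---|---|---|
| 82/103 = 79.6% | 16 of 26 (q about 60%) | 98/129 = 76.0% | −3.6 |
| 82/103 = 79.6% | 26 of 26 | 108/129 = 83.7% | +4.1 |
| 98/103 = 95.1% | 16 of 26 | 114/129 = 88.4% | −6.8 |
| 98/103 = 95.1% | 26 of 26 | 124/129 = 96.1% | +1.0 |

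With the SAP prior, the first scenario gives 79.9% (71.8 to 87.0) for the protocol rate, against 76.3% (68.6 to 83.1) and 83.9% (77.2 to 89.7) for the two pooled rates. The intervals overlap widely.

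**4. Rises from assay variation alone.** Assume two-fold dilutions read in duplicate, no true change, and a log2 SD of 0.25 to 1.0. In simulation, the chance of a ratio above 1 is about 14% to 42%, depending on the SD and on how much error the duplicates share. It is 3% to 36% for at least 2-fold and 0% to 15% for at least 4-fold. On a continuous readout with symmetric error, the chance of a ratio above 1 is 50%.

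If seropositives rise only by noise, 21% of 26 is about 5 and 14% is about 4:
- First scenario: 87/129 = 67.4% (−12.2) or 86/129 = 66.7% (−12.9).
- Second scenario, 5 rising: 103/129 = 79.8% (−15.3).
- First scenario at the noisy end, 42% or about 11 rising: 93/129 = 72.1% (−7.5).

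**The case against.** The best defence is that the SAP was entitled to do this and did it openly. Protocol 10.3.1 says of the SAP: "This document will provide further details regarding the definition of analysis variables". The endpoint wording in Protocol 4.2.1 has no serostatus limit. The protocol never says which result makes a subject seronegative. If N antibody decides, an N-negative subject already at or above the RBD LLOQ on Day 1 would count without any rise, which the SAP rule prevents. The 2-fold and 4-fold rates reduce the noise count, and the trial was halted at 129 subjects with no inference planned.

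Much of this stands. It limits the seriousness and argues for defining seronegative by the same assay. But supplying further detail does not cover an unexplained change to a denominator and threshold that 10.3.5.2 states outright, and the SAP's own lead-in still contradicts the new rule.

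A reader might also infer more than the documents support:
- **That the change was concealed.** SAP 6.0 sends changes to the change log, and the log states this one. SAP 6.4 is headed as changes from protocol version 2.0 to the amendment, and the amendment does not touch seroconversion, so its silence there proves little.
- **That SAP 6.3 contradicts the change by saying definitions remain.** That depends on SAP version 1.0, which is not available here.
- **That the rate is inflated.** The sign depends on q and p.
- **That the split cannot be recovered.** The symptom exclusion in 12.7.3 applies to the asymptomatic-infection table, and the 6.4 line on confirmed cases does not limit the Appendix 4 listings, which hold the subject-level RBD, neutralizing and N results.
- **That the tables certainly omit serostatus.** The titles omit co-morbidity too, although 12.0 requires it, and the shells are a separate document. The firmer evidence is the silence of 12.0 and 12.7.2.

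**Conclusion.** The point holds. The SAP's primary Day 43 rate and the protocol's rate are different quantities, and the planned text does not present the protocol's. The SAP also contradicts itself between 10.8.1 and its subsections.

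The size cannot be fixed from the documents. At an assumed 20% seropositive share, the shift runs from about −7 to +4 points over the two scenarios when 60% to 100% of seropositives rise. It can exceed 12 points downward if they rise only by noise. It is zero if nobody has quantifiable antibody on Day 1, or if seropositives rise as often as seronegatives convert. Locating the difference wholly in seropositive subjects assumes that the half-LLOQ substitution is made on the final titre.

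No test decision is at risk. The matter is worth fixing because the primary figure would otherwise carry a name that the protocol defines differently.

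**What to change.** In SAP 10.8.1, 10.8.1.1, 10.8.1.2 and 12.7.2:

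1. Report the Day 43 proportion with titre at or above the LLOQ among subjects seronegative on Day 1, labelled as the protocol-defined rate. Define seronegative as the same assay's Day 1 titre below the LLOQ, so that nobody counts without a rise, and show Day 1 N status alongside.
2. Show baseline-seropositive subjects separately by GMFC, with the 2-fold and 4-fold rises, and restore GMC/GMT by baseline serostatus. The Overall column is enough: seven strata average 129/7, about 18 subjects by main condition.
3. If the rule of a ratio above 1 is kept, label it an any-rise row, give the reason, and align the 10.8.1 lead-in with its subsections.
4. State in 10.5 or 10.8.1 that the half-LLOQ substitution applies to the final reported titre.

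**Cost.** SAP wording, one flag from Day 1 titres already collected and listed, and extra rows in planned tables; no new data. The price is a smaller denominator for the protocol-defined rate and sparse seropositive rows, above all in the neutralizing-antibody subset.
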